12.11 Hand Grip Test

One of the most common methods of measuring muscle strength is the isometric grip strength test. We will measure isometric grip strength using a handgrip dynamometer (JAMAR®, Nottinghamshire, UK). The test will be performed in the sitting position with the shoulder of tested arm adducted, the elbow flexed at 90°, whereas the forearm and wrist were set in neutral position ²⁶. The testing protocol consists of three maximal isometric contractions for 5 s, on both hands, with a rest period of at least 60 s and the highest value will be used for determination of maximal grip strength. The subjects will be instructed to squeeze the dynamometer as hard as possible.

12.12 Pulse wave analysis

Radial Pulse wave analysis (PWA) and carotid-femoral pulse wave velocity (PWV) will be performed using the Sphygmocor tonometry system (AtCor Medical, Sydney, Australia) and assessed as previously described²⁷. Participants will be in the supine position. Briefly, a central aortic pressure waveform will be derived from a measured radial artery pressure waveform. Aortic augmentation index (Aix) will be calculated as the difference between the first and second systolic peaks of the ascending aortic waveform divided by the difference between central aortic systolic blood pressure (SBP) and central aortic diastolic blood pressure (DBP). Aix will be standardized to a heart rate of 75 beats/minute (Aix75). To determine PWV, ECG-gated pulse pressure waveforms will be obtained sequentially over the right carotid artery and the right femoral artery. PWV will be calculated as the transit distance between the measurement

sites divided by the transit time computed as the time interval between the feet of the two pressure waves.

12.13 Echocardiogram (ECG)

A 12-lead ECG will be performed by a co-investigator or delegated staff. The ECG print out must be interpreted, signed and dated by a co-investigator.

12.14 Buccal mucosa sampling

Perform mouth wash with distilled water (three replicates) to remove traces of saliva and surface mucous. Then perform exfoliation within the two cheeks to maximize the cell sample and remove any trace unknown, which may be caused by sampling of only one cheek. The exfoliation should use a disposable brush similar to that used for Pap smear, performing 10 rotations of the brush against the inner wall of the cheeks starting in the centre and gradually increasing the circumference, producing a spiral effect to increase the sampling of a larger area and prevent erosion continuous of a single region. After exfoliation, the brushhead must be placed in a container (test tube) with 0.4ml of buffer containing: 0.01 M Tris hydrochloride (Tris HCl), 0.1 M acid ethylenediaminetetraacetic (EDTA) and 0.02M Sodium Chloride (NaCl) with pH 6.8, turning in the way that the cells are released and displaced on the inner edge of the container²⁸.

The micronucleus (MN) assay in exfoliated buccal cells is a useful and minimally invasive method for monitoring genetic damage in humans²⁹. The Buccal Micronucleus Cytome (BMCyt) assay is a minimally invasive method for studying DNA damage, chromosomal instability, cell death and the regenerative potential of human buccal mucosal tissue. This method is increasingly used in molecular epidemiological studies for investigating the impact of nutrition, lifestyle factors, genotoxin exposure and genotype on DNA damage, chromosome malsegregation and cell death. The biomarkers measured in this assay have been associated with increased risk of accelerated ageing, cancer and neurodegenerative diseases³⁰.

12.15 Blood sampling and storage

Over the study in those participating in the cohort study only in total approximately 150 ml of blood will be taken to determine the parameters outlined above, in those also participating in the RCT in total (cohort study and RCT) approximately 200 ml of blood will be drawn. A potential remainder of serum and plasma will be stored anonymised (patient number and visit number only) at -80°C in the Biobank

of the Medical University of Graz for potential future analyses. Therefore subjects will be asked to sign the informed consent of Biobank.

12.16 Faeces sampling

Sampling will be performed using two stool collection tubes by Sarstedt, Nümbrecht, Germany, using a stool collector (Süsse Stuhlfänger, Gudensberg, Germany). One tube will be used for native stool, the other prefilled with stool DNA-stabilizer for collection of DNA-stabilized stool specimen. Directions for safe and hygienic fecal collection will be delivered to the probands in words as well as in pictograms. Bacterial DNA will be extracted from saliva and stool samples using the MagNA Pure LC DNA Isolation Kit III (Roche). The 16S rRNA gene will be amplified in a PCR reaction and sequenced with next-generation sequencing technology (Roche Genome Sequencer FLX or Illumina MiSeq) and interpreted by the respective software analyzers.

12.17 Saliva sampling

Saliva will be collected by Salitubes (DRG Instruments Marburg, Germany) using a routine method for saliva collection and dedicated tubes as well as standardized instructions for the collection. Hormones and salivary microbiome will be analysed by methods described in 12.4 (adapted ELISAs by BSM, Vienna, Austria) and 12.16, respectively.

12.18 Continuous glucose monitoring

Minimally invasive CGMS will be performed using the Abbott FreeStyle Flash or Medtronic Ipro 2 glucose monitoring device. This system eliminates the need for routine finger pricks, reading glucose levels through a sensor that can be worn on the back of the upper arm for up to 7-14 days. In addition, no finger prick calibration is needed—a key differentiator from current continuous glucose monitoring systems. Both, Abbott's FreeStyle Flash and Medtronic Ipro 2 glucose monitoring systems, consist of a small, round sensor—approximately the size of a two Euro coin—worn on the back of the upper arm, which measures glucose every minute in interstitial fluid through a small (5mm long, 0.4mm wide) filament that is inserted just under the skin and held in place with a small adhesive pad. A reader is scanned over the sensor to get a glucose result painlessly in less than one second. Scanning can take place while the sensor is under clothing, making testing more discreet and convenient. Each scan displays a real-time glucose result, a historical trend and the direction the glucose is heading. The reader holds up to 90 days of data, providing a historical snapshot of glucose levels over time. The Medtronic devices

requires regular (at least twice daily) calibration measurements with a common glucose measurement device.

In the cohort study the CGM sensor will be used once (14 days, at visit 1) and in those subjects participating in the pilot intervention trial, CGM will be used a second time (another 14 days, CGM will be started at visit 3).

12.19 Physical examination

Physical examination will be performed at visit 1 and include examination of:

- General appearance
- Head, ears, eyes, nose, throat, neck
- Cardiovascular system
- Respiratory system
- Skin
- Thyroid gland
- Musculoskeletal system
- Central and peripheral nervous system

12.20 Vital signs

Systolic and diastolic blood pressure measured in mmHg will be collected at both visits to the trial site. The blood pressure should be measured in a sitting position, with legs uncrossed, the back and arms supported. Subjects should be sitting for at least five minutes before the measurement is taken and subjects should not talk during the measurement. Pulse as beats per minute will be recorded after resting for five minutes in a sitting position. The pulse should be measured at both study visits to the trial site.

12.21 Echocardiography

Echocardiographic examination will be performed with a Vivid 7 (GE Healthcare, Chalfont St Giles, UK). For acquisition of images in the parasternal view the participant will be placed in the steep left-lateral decubitus position. The participant's left arm will be raised. Images will be acquired during quiet respiration. Image rate will be at least 30 frames per second.

12.22 International physical activity questionnaire (IPAQ)

IPAQ will be used in the current study. This tool was developed for measuring physical activity in 1998 and was followed by extensive reliability and validity testing undertaken across 12 countries (14 sites)

during 2000^{31, 32}. The final results suggested that this tool had acceptable measurement properties for use in many settings and in different languages and was suitable for national population-based prevalence studies of participation in physical activity. The short version of IPAQ tool will be used in the current study. The tool includes a set of 4 questionnaires. The questions asked about the time spent being physically active in the last 7 days.

12.23 Bioelectrical impedance analysis (BIA)

Bioelectrical impedance analysis is a fast, reliable, affordable and non-invasive technique to measure body composition. Its accuracy and dependability have been scientifically proven^{33, 34} and clinically demonstrated time and time again. It uses the fact that tissue types differ in electric conductivity. Bones and fat, for instance are bad conductors. Skeletal muscles on the other hand, due to their water and electrolyte content, have much lower impedance. BIA makes it possible to precisely determine the distribution of the individual components, e.g. fluids (“water”), muscle mass and fatty substance in the body.

12.24 Dry eye assessment

Recent findings show that dry eyes syndrome (“Sicca” syndrome) is tightly regulated by the metabolic and inflammatory factors both on the eye surface and on a systemic level during aging³⁵. Since we propose intermittent fasting besides caloric restriction³⁶ as one of the most significant interventions into the human metabolism, we will conduct the preliminary evaluation of the effects of intermittent fasting on several main clinical parameters of the Sicca syndrome. As part of our trial we will investigate:

- redness of cornea and the stability of basal tear film by using Oculus Keratograph 5M
- the degree of epithelial damage on the eye surface by fluorescein staining
- the tear volume by Schirmer’s test I
- the quantity and the quality of the meibomian gland’s secretion
- the metabolome of basal tear fluid by mass spectrometry
- the risk factors and symptoms of the Sicca syndrome by using the OSDI (Ocular Surface Diseases Index) questionnaire.

All procedures are carried out under non-invasive conditions and lead to no influence of the eye function of the participant, both in short and long term. By analysing the effects of intermittent fasting on the development of dry eyes syndrome, we want to examine the potential of such a treatment as a preventive and possibly even interventional method to sustain and improve eye health during aging.

12.25 Flow mediated dilatation (FMD)

Endothelium-dependent FMD following reactive hyperaemia is examined in the brachial artery according to the guidelines described by Corretti et al³⁷. Using high resolution ultrasound measurements of the right brachial artery are taken after resting and after cuff deflation (250 mmHg for 5 minutes) of the forearm. Scans of the brachial artery are taken proximal to the antecubital fossa with simultaneous ECG recording. Diameter measurements are taken from one media-adventitia interface to the other for three to four times at baseline (the average is taken for calculating the baseline diameter) and three times after 45 to 60 seconds after cuff deflation following reactive hyperaemia. FMD-diameter is calculated as the average of the three diameter measurements following reactive hyperaemia. The dilatation is calculated as the percent change in diameter compared to baseline.

12.26 Data analysis and sample size estimation

Data analysis

Statistical Analyses for primary and secondary outcomes as well as for baseline values are done in a descriptive and exploratory way.

Continuous variables will be summarized with standard descriptive statistics tables and represented graphically with displays such as box plots and histograms, and categorical variables will be described by frequency tables and standard graphical displays like bar plots. Scatterplots are used to illustrate possible correlations between the variables.

To examine differences between groups at baseline and following visits, Student's T-tests or Mann-Whitney U tests and chi-square tests will be used as appropriate. Comparisons within groups will be performed using paired T-test or Wilcoxon rank-sum test. A p-value of <0.05 is considered to indicate statistical significance, whereas appropriate correction for multiple testing like Bonferroni Correction or false discovery rate (*Benjamini and Hochberg*) will be applied. To investigate multiple relations generalized linear mixed models will be built to investigate changes between groups and over time, as the physiological changes are represented in various parameters. For high-dimensional "omics-" data appropriate multivariate modelling like Random Forests and Partial Least Squares Regression will be used to elucidate differences between groups and time-points concerning potential molecular markers regarding aging effects.

A statistical analysis plan will be prepared and finalized before database lock. All statistical analysis will be done in R (version 3.0.1.).

Sample size estimation

Data on the effects of ADF on metabolic parameters, human physiology, aging process and molecular cellular processes in healthy subjects is very limited and a therefore an accurate sample size estimation impossible. However, we reviewed available data and used data on insulin sensitivity from a similar, albeit not entirely comparable study population with a HOMA-IR of 3 ± 1.1 (mean \pm SD)⁷. Assuming a power of 80% and a type I error rate of 5%, we would need 50 subjects per group to demonstrate an effect size of 15%, which has been demonstrated previously³⁸. Therefore the sample size of 50 subjects in the ADF and 50 subjects in the control group, as chosen for our cohort study, seems to be reasonable. In addition, previous publications have also suggested a sample size of 50 subjects per group for such types of studies with insufficient details about the outcome parameters required for a sample size estimation³⁹. Subjects in the control group will be asked to participate in a pilot, randomized controlled trial, where they are randomized to either ADF or continuing in the control group. We expect an acceptance rate of about 40%, hence a sample size of about 10 participants per group.

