8.3 Primary outcome measures in the randomized controlled trial

[figure not shown]
- Difference in the changes of insulin sensitivity (Matsuda index, ISI, HOMA-Index, QUICKI)
- Difference in the change of endothelial function

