8.4 Secondary outcome measures in the randomized controlled trial

- Levels of different cell signalling and cell cycle proteins (p16, p21, p53, NCX, mTOR, Ras, Rb)
- Differences in parameters of cell death (apoptosis, stress resistance, mitochondrial damage) between groups
- Differences in telomere length, double strand breaks, chromosomal aberrations, heterochromatin between groups
- Differences in telomerase activity between groups

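### Section 12.26 does not say which of its listed analyses estimates the RCT's primary difference in change; a baseline-adjusted comparison should be named

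*Protocol*

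**What the plan says.** Section 8.3 gives the RCT primary outcomes as "Difference in the changes of insulin sensitivity (Matsuda index, ISI, HOMA-Index, QUICKI") and "Difference in the change of endothelial function". Both are contrasts between arms in how far participants move from their own starting value.

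Section 12.26 covers the cohort and the RCT together and names three kinds of analysis:

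- Between groups: "To examine differences between groups at baseline and following visits", by t-test, Mann-Whitney U test or chi-square test.
- Within groups: "Comparisons within groups will be performed using paired T-test or Wilcoxon rank-sum test".
- Longitudinal: "generalized linear mixed models will be built to investigate changes between groups and over time", with no model form, covariates or constraint on baseline means.

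The analyses "are done in a descriptive and exploratory way", a p-value threshold of 0.05 with multiplicity correction is set, and a SAP is to follow before database lock. Nothing says which of the three is the analysis for 8.3.

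Under sections 11.1 to 11.3, control participants have an OGTT at Visit 1 and EndoPAT, FMD, REE and BIA at Visit 2. RCT consent is taken at Visit 2. All of these measurements are repeated at Visit 4.

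**The concern.** A two-sample test on Visit 4 values leaves each participant's starting value out. A within-arm before/after test is not a comparison between randomised arms: one arm can be significant and the other not when the arms hardly differ. Neither computes the difference in change that 8.3 names.

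The arms are expected to hold about 10 people each, so chance imbalance at baseline will be large. It passes into a Visit 4 comparison and, through regression to the mean, in the opposite direction into a change-score comparison. The synopsis says the pilot's data are to help design a larger trial. For that use, a precise arm difference with an interval matters more than a set of p-values.

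**Working it through.** **Inputs.** Section 12.26 expects about 40% acceptance and about 10 per arm. This reproduces from its 50 controls: 0.40 × 50 = 20, or 10 per arm. The synopsis's 60 controls give 0.40 × 60 = 24, or 12 per arm. Section 12.26 also gives HOMA-IR 3 with SD 1.1 and a 15% effect: 0.15 × 3 = 0.45 units, or 0.45/1.1 = 0.41 SD. A two-sided 5% level is assumed. The correlation r between baseline and Visit 4 is not in the protocol, so it is varied.

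**Chance imbalance.** The SD of the baseline difference between arms of 10 is √(2/10) = 0.447 SD, or 0.447 × 1.1 = 0.49 HOMA-IR units. That exceeds the 0.45-unit effect. A Visit 4 comparison carries r times the imbalance and a change score carries (r − 1) times it. For a one-SD imbalance at r = 0.7 this is 0.7 × 0.447 = 0.31 SD and −0.3 × 0.447 = −0.13 SD.

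**Variance of the arm difference** (equal SDs at both visits), as a multiple of 2σ²/10:

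- Visit 4 only: 1
- Change score: 2(1 − r)
- ANCOVA: (1 − r²)(1 + 1/(N − 4)), with N = 20, so (1 − r²) × 1.0625

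| r | Visit 4 | Change | ANCOVA | ANCOVA vs Visit 4 | ANCOVA vs change |
|---|---|---|---|---|---|
| 0 | 1 | 2.0 | 1.063 | 6% more | 47% less |
| 0.3 | 1 | 1.4 | 0.967 | 3% less | 31% less |
| 0.5 | 1 | 1.0 | 0.797 | 20% less | 20% less |
| 0.7 | 1 | 0.6 | 0.542 | 46% less | 10% less |
| 0.8 | 1 | 0.4 | 0.383 | 62% less | 4% less |
| 0.9 | 1 | 0.2 | 0.202 | 80% less | 1% more |

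The SE in SD units is √(factor × 0.2). At r = 0.5 / 0.7 / 0.8 it is 0.447 throughout for Visit 4 only, 0.447 / 0.346 / 0.283 for change, and 0.399 / 0.329 / 0.277 for ANCOVA.

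**Break-even with Visit 4 only.** (1 − r²) × 1.0625 = 1 gives r = √(1 − 1/1.0625) = 0.24. Allowing for the lost degree of freedom in the test as well, it is about 0.26.

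**On the HOMA-IR scale** (noncentral t; 18 df, or 17 for ANCOVA). Each cell reads Visit 4 only / change / ANCOVA:

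| r | Detectable difference, 80% power | Power for 0.45 units |
|---|---|---|
| 0 | 1.46 / 2.06 / 1.51 | 13.9% / 9.4% / 13.4% |
| 0.5 | 1.46 / 1.46 / 1.31 | 13.9% / 13.9% / 16.2% |
| 0.7 | 1.46 / 1.13 / 1.08 | 13.9% / 20.1% / 21.7% |
| 0.8 | 1.46 / 0.92 / 0.90 | 13.9% / 27.8% / 28.7% |
| 0.9 | 1.46 / 0.65 / 0.66 | 13.9% / 49.0% / 48.4% |

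With 12 per arm the detectable differences are 1.32 / 1.32 / 1.17 at r = 0.5 and 1.32 / 1.02 / 0.97 at r = 0.7, the same pattern. In simulation (40,000 runs per setting, r from 0 to 0.8) all three tests held type I error between 4.8% and 5.1%.

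**The mixed model.** The OGTT and the endothelial tests have one baseline and one follow-up, at Visit 4. With complete data, an unconstrained arm-by-time linear mixed model then returns the change-score contrast. A model that gives both arms a common baseline mean comes close to ANCOVA. The wording of 12.26 fits either.

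**The case against.** The strongest reply is that 12.26 does plan an analysis of change: the mixed model uses the baseline and can deliver the 8.3 contrast. That stands. A reader might infer that the plan discards the baseline altogether, and the text does not support this. What remains is that 12.26 never ties the model to 8.3 and leaves open the version that gains nothing over change scores.

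A reader might also infer that the protocol orders significance tests at baseline between the randomised arms. It does not say so. The sentence serves the cohort too, where the groups are not randomised and a two-sample comparison at the cohort visits is proper. Likewise, section 8.4 speaks of "Levels of different cell signalling and cell cycle proteins" without mentioning change, but it is a list of measures close to the cohort's list in 8.2, not an analysis that rules out a baseline.

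Calling ANCOVA a free gain would go too far. It loses slightly to a Visit 4-only test when r is below about 0.25, and the larger savings in the table are against that comparator; against change scores they are modest.

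Finally, the work is exploratory, no listed test is invalid, and model detail can go to the SAP, which is not shown. Silence on covariates would therefore be no finding. But 12.26 is not silent: it fixes specific tests, two of which do not estimate the stated primary outcome.

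**Conclusion.** The point holds as a mismatch between 8.3 and 12.26 that should be corrected. Three kinds of analysis are listed, none is assigned to the primary RCT contrast, and two do not estimate it. The loss is one of precision, not validity. At 10 per arm, ANCOVA cuts variance by 20% / 10% / 4% against change scores and by 20% / 46% / 62% against Visit 4 only, at r = 0.5 / 0.7 / 0.8.

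These figures assume r, equal SDs at both visits and a linear relation. They also assume that the Visit 1 and Visit 2 measurements precede allocation. The protocol does not state the moment of randomisation; this is inferred from RCT consent being taken at Visit 2.

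With r unknown, ANCOVA is the safer choice: over r from 0 to 0.9 its worst penalty is about 6% in variance, against a doubling for change scores at r = 0. It does not rescue the pilot's power. For the 15% effect, power is about 13% to 29% for r from 0 to 0.8, and 48% at r = 0.9.

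**What to change.** In section 12.26, add a short paragraph for the RCT:

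- The between-arm effect at Visit 4 is estimated by ANCOVA, with arm and the participant's own pre-randomisation value as covariates, or by a mixed model with a common baseline mean. It is reported with a 95% CI. The arm coefficient is the same whether the response is the Visit 4 value or the change, so it answers 8.3 directly.
- The baseline visit for each measure is named (Visit 1 for the OGTT, Visit 2 for EndoPAT and FMD), with confirmation that it precedes randomisation.
- Within-arm tests are descriptive only.
- Between-group tests at baseline apply to the cohort comparison, not to the randomised arms.

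Further model detail can go to the SAP. The cost is a few sentences and one residual degree of freedom, with no new data. The possible downside is the small loss of precision at low r shown above.

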3. AMENDMENT HISTORY

Amendment No.	Protocol Version No.	Date issued	Author(s) of changes	Details of Changes made
1	1.2	10.04.2015	[name], [name]	Glucose monitoring device was added (MedTronic Ipro 2)
2	1.3	13.05.2015	[name], [name]	Bioelectrical impedance analysis (BIA) was added
3	1.4	03.07.2015	[name], [name]	Dry eye assessment, Ocular Surface Disease Index Questionnaire
4	1.5	22.09.2015	[name], [name]	Changes in inclusion criteria (body mass index:22.0-30.0kg/m ²)
5	1.6	10.02.2016	[name], [name]	FMD (Flow Mediated Dilatation) was added
6	1.7	13.03.2016	[name], [name]	Number of patients was reduced from 100 to 90.

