4. SYNOPSIS

Study title	InterFast
Study design	Cohort study with an embedded randomized controlled pilot trial
Study participants	Healthy subjects and subjects who do already practice Alternate Day Fasting
Number of participants	90 (30 Participants in Alternate Day Fasting group and 60 participants in the control group). Those participants in the control group will be asked to participate in a short randomized controlled trial, where they will be either allocated to an Alternative Day Fasting group or another control visit.
Planned duration	18 months
Primary objective	The primary objective is to elucidate in which extent alternate day fasting influences human physiology in healthy individuals in both, the short and long term. Data of the pilot RCT will help to design a larger trial investigating Alternate Day Fasting in various groups of interest.
Secondary objectives	The secondary objective of this study is to define novel molecular markers of aging and age-related diseases.

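### Student's t-test is named for a cohort of 30 versus 60, so its 5% error rate holds only where the two groups have similar SDs; Welch's test removes that dependence at almost no cost

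*Protocol*

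**What the plan says.** Protocol section 12.26 (Data analysis) covers differences between groups at baseline and at later visits with one sentence: "Student's T-tests or Mann-Whitney U tests and chi-square tests will be used as appropriate". No unequal-variance test is named. The same section sets the threshold ("A p-value of <0.05 is considered to indicate statistical significance"), promises "appropriate correction for multiple testing like Bonferroni Correction or false discovery rate", and describes the status of the work: "Statistical Analyses for primary and secondary outcomes as well as for baseline values are done in a descriptive and exploratory way". It also states that "A statistical analysis plan will be prepared and finalized before database lock".

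The group sizes are not consistent:

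- The synopsis (section 4) gives "90 (30 Participants in Alternate Day Fasting group and 60 participants in the control group".
- The amendment history (section 3), amendment 6, records that "Number of patients was reduced from 100 to 90", without a split.
- Section 10.1 still describes 100 subjects, fifty of them already fasting.
- The sample size paragraph of 12.26 still rests on 50 per group.

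The 50/50 figures add up to the total that amendment 6 replaced, so 30/60 is the best reading of the current design.

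**The concern.** Student's two-sample test in its ordinary form estimates one common variance from both groups. With equal group sizes, unequal SDs hardly matter. With 30 against 60, the common estimate is dominated by the controls. If the smaller ADF group varies more, the standard error is too small and false positives exceed 5%. If it varies less, the standard error is too large and power is lost.

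The primary cohort outcomes in section 8.1 are of very different kinds: body composition, energy expenditure, insulin indices, glucose patterns, vascular measures, blood pressure and hormones. Equal SDs cannot be presumed for all of them. Each continuous comparison made with this test is therefore exposed, although it is distorted only where the SDs do differ.

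**Working it through.** **Inputs from the protocol.** Group sizes 30 (ADF) and 60 (control), from the synopsis. Significance threshold 0.05, from 12.26; sidedness is not stated and two-sided is assumed. The only SD given is 1.1 for HOMA-IR (12.26), from one outside population and not split by group.

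**Assumption.** The ADF/control SD ratio r is not in the protocol. The range 0.5 to 2 is shown, with 0.8 to 1.25 as a moderate band. Data are normal and the true means equal.

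**Step 1: formulas.** Set the control SD to 1.

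- True variance of the mean difference: r²/30 + 1/60.
- Variance that the pooled test expects: [(29r² + 59)/88] × (1/30 + 1/60) = [(29r² + 59)/88] × 0.05.

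**Step 2: worked values.**

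- r = 1: true 0.0500, pooled 0.0500. The test is correct.
- r = 1.5: true 2.25/30 + 1/60 = 0.0917. Pooled (65.25 + 59)/88 × 0.05 = 1.412 × 0.05 = 0.0706. The ratio is 1.30, so the standard error is too small by a factor of √1.30 = 1.14. The critical value 1.987 (88 df) then acts like 1.987/1.14 = 1.74, which gives an error of roughly 8%.
- r = 0.8: true 0.64/30 + 1/60 = 0.0380. Pooled (18.56 + 59)/88 × 0.05 = 0.0441. The ratio is 0.86, so the standard error is too large.
- At 50/50 the pooled variance is (r² + 1)/50, which equals the true variance for every r. The exposure comes from the 1:2 split.

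**Step 3: simulation.** True two-sided error at nominal 5%, with 400,000 simulated null trials per setting for the t-tests and 40,000 for Mann-Whitney:

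| SD ratio ADF/control | Student, 30/60 | Welch, 30/60 | Mann-Whitney, 30/60 | Student, 50/50 |
|---|---|---|---|---|
| 0.5 | 1.7% | 5.0% | 3.2% | 5.1% |
| 0.8 | 3.5% | 5.0% | 4.3% | 4.9% |
| 1 | 5.0% | 5.0% | 4.9% | 5.0% |
| 1.25 | 6.8% | 5.0% | 6.1% | 5.0% |
| 1.5 | 8.5% | 5.0% | 6.9% | 5.0% |
| 2 | 11.0% | 5.0% | 8.6% | 5.1% |

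The protocol's nominal 5% is reproduced at equal SDs. Independent runs agree within about 0.1 to 0.2 points for the t-tests and a few tenths for Mann-Whitney.

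**Step 4: does a multiplicity correction help?** Take Bonferroni over the seven bullets of section 8.1 as an illustration (0.05/7 = 0.71%). Student's true error is then about 1.2% at r = 1.25, 1.8% at r = 1.5 and 2.9% at r = 2, that is 1.7, 2.5 and 4 times nominal. At r = 0.5 it is 0.11%. Welch stays at about 0.7%. The correction does not repair the test.

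**Step 5: price of Welch when the SDs are equal.** For an assumed true difference of 0.64 SD, chosen because it gives about 80% power at 30/60, Student has 80.9% and Welch 80.4%.

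**The case against.** **The test is not fixed.** The sentence offers a choice as appropriate, never says pooled or equal variance, and an SAP is still to come. A t-test variant is often settled there. This stands in part: the SAP can cure the point. But the protocol does name a test, the choice is between two procedures that both drift when spread and group sizes are unequal, and an SAP that follows the wording takes the problem over.

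**Unequal SDs are not documented.** This stands fully. The 8.5% and 11% need an ADF SD of 1.5 to 2 times the control SD, and nothing in the protocol supports that. A reader might infer that the ADF group is the more variable one because it mixes fasting histories. The protocol does not show this: section 6 describes fasters who have kept to the regimen for a set time, both groups meet the same eligibility limits (10.3), and they are to be matched at least on sex, weight and age (10.1). Below a ratio of 1 the test errs on the conservative side.

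**The consequence is limited.** A reader might also infer that every primary outcome will carry wrong p-values and confidence intervals. That goes too far. The error arises only where SDs differ and Student's test is the one used. Section 12.26 mentions no confidence intervals, also plans mixed models and graphical summaries, and calls the analyses descriptive and exploratory. No confirmatory 5% claim rests on this test, although a significance threshold is still set for the primary outcomes.

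**Conclusion.** The point holds as a minor one. With 30 versus 60, the named t-test keeps 5% only where the group SDs are similar. For ratios of 0.8 to 1.25 the true error is about 3.5% to 6.9%, a modest departure. For 0.5 to 2 it is about 1.7% to 11%. Mann-Whitney moves in the same direction, and Welch stays near 5%.

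These figures assume normal data, a two-sided 5% level, the pooled form of Student's test, and 30/60 as the current design. At 50/50, as sections 10.1 and 12.26 still read, the issue disappears. The SD ratios are assumptions, so neither the size nor the direction of an error in this study can be stated.

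**What to change.** In section 12.26, or in the SAP before database lock, replace Student's t-test with Welch's unequal-variance t-test for the cohort group comparisons. Do not rely on Mann-Whitney as a safeguard against unequal spread.

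Reconcile the group sizes: bring section 10.1 and the sample size paragraph of 12.26 into line with the 30/60 of the synopsis, and state the split that amendment 6 left out.

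The cost is one sentence on the test and the correction of two passages. No extra data are needed, and about half a percentage point of power is lost if the SDs are equal. Heteroscedasticity-consistent standard errors in regression models and log-scale analysis of skewed measures such as HOMA-IR are reasonable options but are not needed to settle this point.
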